APPENDIX A. INFORMATION REGARDING EFFECTIVENESS OF CONTRACEPTIVE METHODS AND DEFINITIONS

Definitions
WOCBP: A woman who is considered fertile following menarche and until becoming postmenopausal unless permanently sterile (see below). Women in the following categories are not considered WOCBP: 
• Premenarchal• Premenopausal with 1 of the following:^a
– Documented hysterectomy– Documented bilateral salpingectomy– Documented bilateral oophorectomy• Postmenopausal
– A postmenopausal state is defined as no menses for 12 months without an alternative medical cause.
○ A high FSH level in the postmenopausal range may be used to confirm a postmenopausal state in women not using hormonal contraception or HRT. However, in the absence of 12 months of amenorrhea, confirmation with 2 FSH measurements in the postmenopausal range is required.– Females on HRT and whose menopausal status is in doubt will be required to use 1 of the nonhormonal, highly effective contraception methods if they wish to continue their HRT during the study. Otherwise, they must discontinue HRT to allow confirmation of postmenopausal status before study enrollment.
For male participants of reproductive potential ^b
The following methods during the Protocol-defined timeframe in Section 5.1 are highly effective: 
• Use of a male condom plus partner use of an additional contraceptive method when having penile-vaginal intercourse with a woman of childbearing potential who is not currently pregnant.• Vasectomy with medical assessment of the surgical success (verified by site personnel's review of the participant's medical records)• Sexual abstinence^c
– Abstinence from penile-vaginal intercourse
The following are not acceptable methods of contraception: 
• Periodic abstinence (calendar, symptothermal, post ovulation methods), withdrawal (coitus interruptus), spermicides only, and lactational amenorrhea method.• Male condom with cap, diaphragm, or sponge with spermicide.• Male and female condom used together.
Note: Men with a pregnant or breastfeeding partner must agree to remain abstinent from penile-vaginal intercourse or use a male condom during each episode of penile penetration.

For female participants who are WOCBP

The following methods during the Protocol-defined timeframe in Section 5.1 that can achieve a failure rate of less than 1% per year when used consistently and correctly are considered as highly effective birth control methods:

- Combined (estrogen and progestogen containing) hormonal contraception associated with inhibition of ovulation^d
 - oral
 - intravaginal
 - transdermal
- Progestogen-only hormonal contraception associated with inhibition of ovulation^d
 - oral
 - injectable
 - implantable^e
- Intrauterine device^e
- Intrauterine hormone-releasing system^e
- Bilateral tubal occlusion^e
- Vasectomized partner^{e,f}
- Sexual abstinence^c

FSH = follicle-stimulating hormone; HRT = hormone replacement therapy.

^a Documentation can come from the site personnel's review of the participant's medical records, medical examination, or medical history interview.

^b If the male participant has a partner with childbearing potential, the partner should also use contraceptives.

^c In the context of this guidance, sexual abstinence is considered a highly effective method only if defined as refraining from heterosexual intercourse during the entire period of risk associated with the study treatments. The reliability of sexual abstinence needs to be evaluated in relation to the duration of the clinical study and the preferred and usual lifestyle of the participant.

^d Hormonal contraception may be susceptible to interaction with the investigational medicinal product, which may reduce the efficacy of the contraception method. In this case, 2 methods of contraception should be used.

^e Contraception methods that in the context of this guidance are considered to have low user dependency.

^f Vasectomized partner is a highly effective method of avoiding pregnancy provided that partner is the sole sexual partner of the WOCBP study participant and that the vasectomized partner has received medical assessment of the surgical success.

Source: [Clinical Trials Facilitation and Coordination Group 2020](#).

APPENDIX B. LIST OF PARENT PROTOCOLS

INCB 54828-101 (FIGHT-101)

INCB 54828-201 (FIGHT-201)

INCB 54828-202 (FIGHT-202)

APPENDIX C. COVID-19 PANDEMIC MITIGATION STRATEGIES AND INSTRUCTIONS

The COVID-19 global pandemic presents challenges to the ongoing conduct of clinical trials. In line with regulatory guidance regarding clinical trial execution during the pandemic, the sponsor has issued the following Protocol considerations to ensure participant safety is maintained and adequate benefit/risk analyses are applied relative to participation in the study and the completion of study procedures and objectives while maintaining the investigational product supply chain.

Recognizing the dynamic nature and flexibility required to manage the impact of the pandemic on this clinical trial, additional details will be incorporated into respective study manuals and site-specific monitoring plans as applicable, with institutional requirements as warranted, and communicated and discussed with investigative sites as needed. Relevant test results will be documented in the eCRF, and applicable changes to the ICF will be made and monitored.

Given the critical medical need for alternative treatments for patients in the setting of recurrent advanced/metastatic endometrial cancer and the importance of continuing cancer research, a positive COVID-19 screening test should not result in definitive exclusion. Participants with a positive COVID-19 test during screening may be reassessed for eligibility in the study only after normalization of their COVID-19 screening test and clinical recovery as per the investigator's evaluation.

SARS-CoV-2 Infection and Participation in the Study

Benefit/risk assessment in the context of the COVID-19 pandemic is provided in Section 2.3.1. During the COVID-19 pandemic, additional risks to participants exist either related to going to a health care facility or as a result of study-related activities. It is at the principal investigator's discretion to balance the risk/benefit while considering the participant's safety, existing comorbidities, and current malignancy. In addition, country-specific requirements are to be followed with regard to COVID-19 testing.

Study Site Visits

If local travel restrictions, isolation requirements, or the investigator's benefit/risk assessment determines it to be unsafe for participants to attend study visits at the investigational site, the site staff may elect to pursue the following:

- In order to minimize participant risk, study visits may be conducted via telemedicine modalities (phone or video) or as per site institutional guidelines. At a minimum, a review of AEs and concomitant medications must be completed. On-site visits should be conducted whenever feasible and are required for administration of study treatment. The participant may also be asked to undergo additional safety laboratory assessments.

- In order to support investigator oversight of participant safety and disease management, the participant may be asked to undergo some laboratory tests or study procedures (eg, imaging) at a local laboratory or facility closer to the participant's residence rather than at the investigational site. In this case, the study physician will provide the participant with the list of parameters to be checked. These tests should be performed in certified laboratories and ensure data may be transferred to the investigational site.
- Some tests, such as ECG or computed tomographic scan assessments, may require longer windows due to the COVID-19 pandemic and may be performed outside the regularly scheduled visit window or may be conducted at the next scheduled visit. It is the investigator's responsibility to check with the facility (if performed at a different facility) that the data will be obtained and available for evaluation. General procedures performed outside of protocol time windows will be captured as protocol deviations due to COVID-19 in the eCRF.

Study Treatment Management in the Event of SARS-CoV-2 Infection

If a participant develops a SARS-CoV-2 infection, the event should be reported as an SAE (if it meets the SAE definition requirements) and appropriate medical intervention provided.

Postbaseline COVID-19 testing should follow country-specific requirements depending on the extent of the COVID-19 pandemic, local institutional guidance, or the investigator's clinical judgment. For participants who are diagnosed with COVID-19 during the study (positive COVID-19 test) or presumed (test pending/clinical suspicion) to be affected by SARS-CoV-2 infection, study treatment should be delayed until COVID-19 test normalization and clinical recovery. Prior to restarting treatment, the study medical monitor should be notified regarding the participant's condition; that is, the participant should be afebrile for 72 hours and SARS-CoV-2-related symptoms (if any) should have recovered for a minimum of 72 hours.

Safety monitoring following COVID-19 infection should be implemented as per institutional guidance or clinical judgment (eg, coagulation factors). Concomitant medication administered for treatment of SARS-CoV-2 infection should be carefully considered for potential drug-drug interactions and recorded in the clinical database (EDC).

COVID-19 Vaccination

Participants may receive the COVID-19 vaccine as long as it is not a live vaccine. A live COVID-19 vaccine requires prior consultation with the medical monitor. COVID-19 vaccination will be captured in the eCRF as a concomitant medication. Administration of study treatment may be delayed to ensure vaccination is completed and acute AEs (if any) are managed. The medical monitor may be consulted if needed.

Clinical Trial Monitoring

Study monitoring visits could be postponed; however, the site monitor and sponsor will continue to employ off-site monitoring practices such as routine communication methods (eg, phone calls, emails, video visits) with the sites to get information on trial progress, participant status, and information on issue resolution. The study monitor may remotely review data entered into the

EDC for accuracy and completeness if allowed by the national regulatory body, investigational site, and/or in compliance with local authorities.

Reimbursement of Additional Expenses

The sponsor will reimburse for any extraordinary expenses, keeping appropriate documentation as evidence (eg, travel expenses for the local laboratory visit[s], the costs of local [proximate] laboratory tests).

Table 1:	Objective and Endpoint	6
Table 2:	Statistical Analysis Plan Versions	16

LIST OF FIGURES

Figure 1:	Study Design Schema	8
-----------	---------------------------	---

LIST OF ABBREVIATIONS

Abbreviations and Special Terms	Definition
AE	adverse event
CRF	case report form
CTCAE	Common Terminology Criteria for Adverse Events
eCRF	electronic case report form
FAS	full analysis set
MedDRA	Medical Dictionary for Regulatory Activities
PT	preferred term
QD	once daily
SAE	serious adverse event
SAP	statistical analysis plan
SOC	system organ class
Study treatment	refers to pemigatinib monotherapy or combination therapy with pemigatinib
TEAE	treatment-emergent adverse event
WHO	World Health Organization

1. INTRODUCTION

This is a Phase 2, open-label, multicenter, rollover study for participants with advanced malignancies currently enrolled in Incyte-sponsored studies of pemigatinib who are continuing to receive clinical benefit from treatment with pemigatinib (monotherapy or in combination).

Section 2 of the Protocol provide a detailed description of the investigational product, background, study rationale for doses to be examined, and potential risks and benefits of treatment with study treatment.

The purpose of this SAP is to provide details of the statistical analyses that have been outlined in the Study INCB 54828-801 Protocol.

2. STUDY INFORMATION, OBJECTIVE, AND ENDPOINT

2.1. Protocol and Case Report Form Version

This SAP is based on INCB 54828-801 Protocol dated 17 MAY 2021 and CRFs approved 08 MAR 2023. Unless superseded by an amendment, this SAP will be effective for all subsequent Protocol amendments and eCRF versions.

2.2. Study Objective and Endpoint

[Table 1](#) presents the study objective and its endpoint.

Table 1: Objective and Endpoint

Objective	Endpoint
To evaluate the long-term safety and tolerability of pemigatinib.	Frequency and nature of AEs and SAEs as assessed by CTCAE v5.0.

3. STUDY DESIGN

This rollover study allows participants from multiple Protocols, who are receiving clinical benefit from pemigatinib as either monotherapy or combination therapy, to continue to be treated following the completion of the parent study (also referred to as parent Protocol). The population for the rollover study should be consistent with the population defined in each parent Protocol. The primary eligibility criterion for a participant to enter the rollover study is participation in an Incyte-sponsored study (parent Protocol) and receiving ongoing study treatment.

[figure not shown]
Participants who have enrolled in a prior study (parent Protocol) with pemigatinib as monotherapy or combination therapy and are assessed by the investigator to continue to benefit from ongoing treatment and who cannot access pemigatinib outside of a clinical trial will be eligible.

Disease assessments will be performed per standard of care, with date of progression reported and safety data collected.

Once a participant has rolled over into this study from a parent study, the database for the parent study will be closed and locked, and the parent Protocol study will be considered completed and closed; however, the participant in the rollover study will still be treated as per the plan outlined in the parent Protocol. The parent Protocols include INCB 54828-101 (FIGHT-101); INCB 54828-201 (FIGHT-201); INCB 54828-202 (FIGHT-202); and INCB 54828-207 (FIGHT-207). The study treatments include pemigatinib, INCMGA00012 (INCB 54828-101 only), and pembrolizumab (INCB 54828-101 only).

The study begins when the first participant signs the study informed consent form. The end of the study is defined as the date of the last visit of the last participant in the study. It is estimated that an individual will participate for approximately 12 months. The study is considered completed when the last participant's last visit has occurred. [Figure 1](#) elaborates on the study design.

Figure 1: Study Design Schema

3.1. Randomization

Not applicable.

3.2. Control of Type I Error

This study will only conduct analyses on safety data with regard to AEs. All statistical analyses are exploratory in nature. Control of Type I error is not applicable.

3.3. Sample Size Considerations

Approximately 20 participants will be enrolled from prior (parent) pemigatinib studies.

No formal sample size calculations will be performed for this study.

3.4. Schedule of Assessments

Refer to Protocol dated 17 MAY 2021 for a full description of all study procedures and assessment schedules for this study.

4. DATA HANDLING DEFINITIONS AND CONVENTIONS

4.1. Scheduled Study Evaluations and Study Periods

4.1.1. Day 1

Day 1 is the date that the first dose of study treatment (pemigatinib as monotherapy or combination therapy) in the rollover study is administered to the participants.

4.1.2. Study Day

If a visit/reporting date is on or after Day 1, then the study day at the visit/reporting date will be calculated as

$$\text{Day \#} = (\text{visit/reporting date} - \text{Day 1 date} + 1).$$

If the visit/reporting date is before Day 1, then the study day at the visit/reporting date will be calculated as

$$\text{Day \#} = (\text{visit/reporting date} - \text{Day 1 date}).$$

A study day of -1 indicates 1 day before Day 1.

4.1.3. Baseline Value

Participants are continually taking study treatments before Day 1 of this study. Baseline is not applicable in this study.

4.1.4. Handling of Missing and Incomplete Dates

In general, values for missing dates will not be handled unless methods for handling missing dates are specified in this section or relevant sections. The original reported dates collected on the eCRF should be used in all relevant listings. The following rules will be used for handling partial dates for analyses requiring dates.

When date of last dose is used in deriving variables such as duration of treatment or TEAE flag, a missing or partial date of last dose will be handled as follows:

- If only the day is missing, then use the earlier date of the last day of the month or the date that the participant discontinued treatment will be used.
- If both the month and day are missing, then the earlier date of 31 DEC of the year or the date that the participant discontinued treatment will be used.
- Otherwise, the date that the participant discontinued treatment will be used as the date of the last dose.

4.1.5. Cycle Length and Duration

Cycle 1 Day 1 is the day that the first dose of study treatment in the rollover study is administered. The scheduled cycle length is 21 days with the first day of each cycle corresponding with the first day of pemigatinib as monotherapy or combination therapy (pembrolizumab or INCMGA00012) administrated in that cycle.

4.2. Variable Definitions

4.2.1. Prior and Concomitant Medication

Prior medication is defined as any nonstudy medication started before the first dose of pemigatinib as monotherapy or combination therapy.

Concomitant medication is defined as any nonstudy medication that is started accordingly:

- Before the date of first administration of pemigatinib as monotherapy or combination therapy and is ongoing throughout the rollover study or ends on/after the date of first administration of study treatment.
- On/after the date of first administration of pemigatinib as monotherapy or combination therapy and is ongoing or ends during the course of study treatment administration.

A prior medication could also be classified as "both prior and concomitant medication," if the end date is on or after the first dose of pemigatinib as monotherapy or combination therapy. In the listing, it will be indicated whether a medication is only prior, only concomitant, or both prior and concomitant.

For the purposes of analysis, all medications will be considered concomitant medications unless the medications can unequivocally be defined as not concomitant.

5. STATISTICAL METHODOLOGY

5.1. General Methodology

Unless otherwise noted, SAS® software (SAS Institute Inc, Cary, NC; v9.4 or later) will be used for the generation of all tables, listings, and statistical analyses. Descriptive summaries for continuous variables will include, but not be limited to, the number of participants, mean, standard deviation, median, minimum, and maximum. Descriptive summaries for categorical variables will include the number and percentage of participants in each category.

Participants will undergo disease assessments according to the institution's standard of care. Disease assessment details will not be captured, with the exception of documenting the date of disease progression. Analyses of efficacy data will not be performed under this SAP.

5.2. Treatment Groups

This is an open-label, multicenter, rollover study for participants with advanced malignancies currently enrolled in Incyte-sponsored studies of pemigatinib who are continuing to receive clinical benefit from treatment with pemigatinib (as either monotherapy or in combination therapy).

Participants will be summarized by initially assigned dose level and overall monotherapy total (pemigatinib monotherapy 6 mg QD, pemigatinib monotherapy 9 mg QD, pemigatinib monotherapy 13.5 mg QD, pemigatinib monotherapy total, pemigatinib 9 mg QD + pembrolizumab 200 mg) in this study.

5.3. Analysis Populations

5.3.1. Full Analysis Set

The FAS will include all participants who received at least 1 dose of study treatment (ie, pemigatinib as monotherapy or combination therapy) in the rollover study.

The FAS will be used for the summary of participant disposition, as well as the listing and summary of demographics.

5.3.2. Safety Population

The safety population will include all participants who received at least 1 dose of study treatment (ie, pemigatinib as monotherapy or combination therapy).

All safety analyses will be conducted using the safety population.

6. BASELINE, EXPOSURE, AND DISPOSITION

[Appendix A](#) provides a list of data displays.

6.1. Demographics and Baseline Characteristics

The following demographics characteristics will be summarized and listed for the FAS: age (at entry into the rollover study), sex, race, and ethnicity.

6.2. Disposition of Participants

The number and percentage of participants who were treated, who were ongoing with study treatment, who discontinued from study treatment with a primary reason for discontinuation, who were still in the study, and who withdrew from the study with a primary reason for withdrawal will be summarized for the FAS.

6.3. Protocol Deviations

Protocol deviations recorded in this study will be listed, if applicable.

6.4. Exposure

For participants in the safety population, exposure to pemigatinib will be summarized descriptively as the following:

- **Duration of treatment with pemigatinib (days):**
Date of last dose of pemigatinib – date of first dose of pemigatinib + 1
- **Pemigatinib dose modifications:**
Number of participants who had pemigatinib dose reduction and interruption

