6. STUDY TREATMENT

6.1. Study Treatments Administered

[Table 5](#) presents the study treatment information. This information is also found in the parent protocol.

Table 5: Study Treatment Information

	Study Treatment 1	Study Treatment 2	Study Treatment 3
Study treatment name:	Pemigatinib (INCB054828)	INCMGA00012 (INCB 54828-101 only)	Pembrolizumab (INCB 54828-101 only)
Dosage formulation:	Oral	IV	IV
Unit dose strength(s) /dosage level(s):	2 mg, 4.5 mg, 9 mg, 13.5 mg	500 mg/500 mg	200 mg
Administration instructions:	Taken by mouth once daily	Administered over 60 minutes once every 4 weeks (Day 1 of a 28-day cycle)	
Packaging and labeling:	Pemigatinib 4.5 mg, 9 mg, and 13.5 mg tablets will be provided in 14-count bottles; 2 mg tablets will be provided in 60-count bottles. Each bottle will be labeled as required per country requirement.	500 mg vials Each vial will be labeled as per country requirement.	Commercially labeled product
Storage:	Room temperature	Stored upright under refrigeration at 2°C to 8°C (36°F-46°F) and protected from light	Stored under refrigeration at 2°C to 8°C (36°F-46°F)
Status of treatment in participating countries:	Approved	Not approved	Approved

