10.3.2. Exposure

Measure of exposure for study treatment will be summarized descriptively using the safety population.

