3.1 Dose Exposure			
3.1.1	Summary of Exposure and Duration of Exposure to Pemigatinib	Safety	X

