2.5 Drug Compliance	
2.5.1	Study Treatment Administration - Pemigatinib

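### Does a pemigatinib-only exposure summary fall short for participants who also receive pembrolizumab?

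*SAP*

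**What the plan says.** Protocol 10.3.2 states: "Measure of exposure for study treatment will be summarized descriptively using the safety population". It names no particular measure and does not ask for each drug separately. Both documents define study treatment in the same way; in the SAP abbreviation list it "refers to pemigatinib monotherapy or combination therapy with pemigatinib". SAP Section 3 goes further and names the drugs: "The study treatments include pemigatinib, INCMGA00012 (INCB 54828-101 only), and pembrolizumab (INCB 54828-101 only". Protocol Table 5 lists the same three.

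SAP 6.4 covers one drug: "For participants in the safety population, exposure to pemigatinib will be summarized descriptively as the following". Its two measures are days from first to last pemigatinib dose, and the number of participants with a pemigatinib reduction or interruption. The displays follow suit: Table 3.1.1 is "Summary of Exposure and Duration of Exposure to Pemigatinib" and Listing 2.5.1 is "Study Treatment Administration - Pemigatinib". Among the summary columns in SAP 5.2 is "pemigatinib 9 mg QD + pembrolizumab 200 mg". SAP 9.1 records no change to the protocol's analyses.

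On compliance, Protocol 6.4 has the sponsor calculate it from accountability and infusion records, while SAP 6.5 marks the topic as not applicable and gives no reason.

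**The concern.** Read in sequence, the SAP appears to drop part of a protocol analysis without saying so. If pembrolizumab is a study treatment and exposure to study treatment is to be summarised, a column labelled with pembrolizumab should show how much of it was given. Protocol 9.3 also requires investigators to judge causality for each drug in a combination. A reader weighing an adverse event in the combination column might therefore want to know whether the participant was still receiving infusions and how many had been given. No planned display is titled to show that. The compliance entry looks like a second silent omission, more so because Appendix A keeps a heading for drug compliance. At stake would be the interpretation of safety findings in the combination group.

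**Working it through.** The documents give no power or precision figure to reproduce here. The check is a comparison of text, a count of displays, and a test of whether any planned result depends on the missing information.

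**1. Count of displays (SAP Appendix A).**
- Tables: 1.1.2, 1.2.1, 3.1.1 and ten in the 3.2 series (3.2.1, 3.2.2, 3.2.3, 3.2.6, 3.2.8, 3.2.15, 3.2.16, 3.2.18, 3.2.19, 3.2.20). 3 + 10 = 13.
- Listings: 2.1.1, 2.2.1, 2.3.1, 2.4.1, 2.4.2, 2.5.1, six in the 2.7 series, 2.11.1 and 2.11.2. 6 + 6 + 2 = 14.
- Titled for administration of pembrolizumab or INCMGA00012: 0 of 13 and 0 of 14. The omission is therefore confirmed. The standard table shells are not available, but the titles and SAP 6.4 agree.

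**2. Does any planned result use partner-drug exposure?**
- Denominators: SAP 7.2.2 reports numbers and percentages of participants in the safety population. No rate per unit of exposure is planned, so neither infusions nor time on pembrolizumab enters a denominator.
- Numerators: 4 of the 8 items in the overall adverse-event summary are specific to pemigatinib (related events, interruption, discontinuation, reduction). The other 4 count events whatever the drug. Neither kind needs an infusion count.
- Objective: the single objective in SAP 2.2 is the long-term safety of pemigatinib. Pemigatinib duration by regimen column is the exposure measure that matches it.

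**3. What is already covered for the partner drug?**
- Protocol 9.3 has the action taken with study treatment recorded for every adverse event.
- Listing 2.7.6 covers events leading to interruption, reduction or discontinuation of study treatment, and its title is not limited to pemigatinib.
- What remains unshown is the number of infusions and the time on the partner drug.

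**4. How much context could be hidden? (illustration only)**
Protocol Table 3 schedules pembrolizumab every 21 days. From Day 1, the number of scheduled infusions in T days is floor((T − 1)/21) + 1. For T = 365 this is floor(364/21) + 1 = 17 + 1 = 18. Two participants with 2 and 18 infusions (2/18 = 11% and 100% of schedule) could both appear as 365 days of pemigatinib. This assumes that infusions can stop while pemigatinib continues. Protocol 6.5 leaves that to the parent protocols, and the documents do not say whether it happens. Even then, no adverse-event percentage would move.

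**5. Compliance.** Protocol 6.4 sits in the study treatment section and describes site conduct and monitoring. Protocol Section 10 lists disposition, demographics, exposure and safety, with no compliance analysis. SAP 6.5 therefore omits nothing that Section 10 promised. The compliance heading in Appendix A holds only the pemigatinib administration listing. Listing numbers skip 2.6 and 2.8 to 2.10, which suggests headings carried over from a template, though that is an inference.

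**The case for a change.** The strongest case for a change is that the protocol sentence is not limited to pemigatinib, SAP Section 3 removes doubt about which drugs count, and SAP 9.1 was the place to declare the narrowing. The information does not surface elsewhere either: SAP 4.2.1 confines the medication listing to drugs other than study treatment, disposition is not specified by drug, and Listing 2.7.6 shows only changes driven by adverse events. In addition, the treatment-emergent window in SAP 7.2.1 runs from the last dose of study treatment. If the last infusion falls after the last pemigatinib tablet, the displays do not show the date needed to check the flag.

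Most of this is factually right. The wording does differ, the difference is undeclared, and one sentence in SAP 9.1 would have been tidier. It does not show that a result goes wrong. The treatment-emergent flag is derived from dosing dates, not from the exposure table. SAP 7.2.1 counts an event as treatment-emergent unless it clearly is not, and all adverse events are listed regardless of timing. The protocol sentence can also be read less strictly: it asks for a measure of exposure to a treatment defined as a regimen, and pemigatinib duration shown by regimen column is such a measure. SAP Section 3 weakens that reading without excluding it.

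**Conclusion.** No change to the plan is needed. This is a small inconsistency of wording between Protocol 10.3.2 and SAP 6.4, and its cost is limited to context. Following the SAP as written leaves every planned percentage and the conclusion about pemigatinib unaffected. The missing context is partner-drug infusion counts and duration for one of five columns, in a descriptive study of about 20 participants. The documents do not say how many are on a combination, and SAP 5.2 plans no INCMGA00012 column.

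Analysts can fill the gap sensibly if it turns out to matter. Appendix A allows its display list to be modified without an amendment when the nature of the analysis is unchanged, so a short listing of infusions could accompany the report. The compliance entry is a clerical loose end of the same kind.

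The conclusion assumes that no exposure-adjusted rate is added later and that the objective stays confined to pemigatinib. The case report forms are not available, so whether infusion quantities are held in the database is unconfirmed; no planned percentage uses those quantities.
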